### 6.2 Pharmacokinetics/Pharmacodynamics

Pharmacokinetic/pharmacodynamic analysis will be performed on the Pharmacokinetic and Pharmacodynamic Populations respectively

Plasma samples will be analyzed for bexagliflozin concentrations using a validated method.

Blood samples for bexagliflozin plasma concentrations will be collected in each period at pre-dose and at 1, 2, 3, 4, 5, 6, 8, 10, 12, 16, 24, 36, and 48 h post dose.

Urine samples will be collected in 12 hr intervals to evaluate the mean UGE.

Urine collection in 12 h batches will be performed at pre-dose (-12 to 0 h on Day 1 and Day 8), and at post-dose at 0 to 12 h, 12 to 24 h, 24 to 36 h, and 36 to 48 h in each treatment period.

### **6.3 Safety**

Safety analysis will be performed on the Safety Population.

The safety profile of bexagliflozin under fasting and fed (high-fat, high-calorie) conditions will be assessed through the recording, reporting, and analyzing of adverse events, clinical evaluations, and laboratory tests.

Safety variables include the following:

1. Adverse events
2. Clinical laboratory measurements – serum chemistry, hematology, and urinalysis
3. Vital signs
4. ECG
5. Physical examination
6. Pregnancy test
7. Concomitant medications/treatments

#### **6.3.1 Study Day and Visit Window Definitions**

Refer to section 6.1.1 for details.

#### **6.3.2 Extent of Exposure to Study Medication**

Subjects who gave consent to participate in the study will be randomly assigned to 1 of 2 treatment groups. Each group will be dosed with bexagliflozin under a fasted state in one period and under a fed state (high fat, high calorie) in the other period. A single oral dose of 20 mg of bexagliflozin will be provided to subjects in each treatment period.

#### **6.3.3 Adverse Events (AEs)**

Adverse events will be collected and coded using version 19.0 (or newer) of MedDRA. Analysis of adverse events will be carried out on the Safety Population. All adverse events will be included in the individual subject data listings. Only treatment emergent adverse events (TEAEs) will be tabulated in summary tables. The incidence of TEAEs will be presented by treatment. If the AE(s) onset date-time or date occurs after the first dose up until right before the next dose, the AE(s) will be assigned to the first treatment. Any AE(s) that occur after the second dose up until study termination will be assigned to the second treatment.

All adverse events will be assessed by the investigator(s) with respect to severity, relationship to study drug and seriousness.

If an AE becomes serious during the course of the study, the initial AE will be reported with an end date equal to the start date of the serious adverse event (SAE) and outcome 'did not resolve'. The SAE start date will be the date the AE became serious.

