5.6 Concomitant Therapy

The participants are not allowed to take any prescription or non-prescription drugs, vitamins, or dietary supplements at any time during 14 days prior to (first) drug administration and for the duration of each study period. No other concomitant medications are permitted with the exception of those required for treatment of an adverse event. Subjects may receive any medications for adverse events that are necessary to control or minimize the likelihood of more serious adverse events in the investigators' judgment.

Concomitant medications administered at the time of randomization and during the study are to be recorded on the case report form (CRF). The medication name, dose, frequency, route of administration, date(s) of administration and reason for administration must be recorded. This documentation should continue until 1 week from the end of the last study product dosing. Medications that a subject receives after entering the study and prior to randomization must be recorded in the CRF.

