6.10 Concomitant Medication Assessments

A concomitant medication is any medication the subject enters the trial taking and is expected to continue taking for some portion of the trial, as well as any medication the subject takes during the course of the trial. All prescription and over-the-counter medications, including vitamins and herbal supplements, that subjects receive during the trial must be documented on the CRF. This documentation should continue until the subjects are discharged.

Concomitant medications will be coded using the World Health Organization Drug Dictionary (WHO-DD). A table of concomitant medications based on the anatomic therapeutic chemical classification (ATC) and preferred name will be produced. A listing of concomitant medications will include all medications taken by any subjects during the course of the study.

Concomitant medications administered during the study are to be recorded on the CRF. The medication name, dose, frequency, route of administration, date(s) of administration and reason for administration must be recorded. This documentation should continue until discharge from the study.

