7.7 Day 8 through 10 Activities (Post-dose)

- For group 1 subjects, after an overnight fast of at least 10 h, bexagliflozin tablets, 20 mg, will be administered 4 h prior to the first meal of the day as detailed in [Section 5.2](#).
- For group 2 subjects, after an overnight fast of at least 10 h, bexagliflozin tablets, 20 mg, will be administered 30 min after the start of the high-fat meal as detailed in [Section 5.2](#).
- Record vital signs at 4 h (day 8) and 48 h (day 10) post-dose.
- Perform 12-lead ECG taken in the supine position after at least 10 min of rest at 4h (day 8) and 48 h (day 10) post-dose.
- Plasma samples will be drawn for PK analysis as detailed in [Section 6.6.2.4](#) at 1, 2, 3, 4, 5, 6, 8, 10, 12, 16, 24 (day 9), 36 (day 9) and 48 h (day 10).
- Urine collection in 12 h batches at 0 to 12 h and 12 to 24 h, 24 to 36 h and 36 to 48 h for analysis of electrolytes, uric acid and creatinine and for UGE (PD) analysis as described in [Section 6.6.2.3](#). Concomitant medications and adverse event information is collected as appropriate.

- On day 10 perform a physical examination as described in [Section 6.3](#).
- On day 10, urine will be collected as described in [Section 6.6.2.2](#) for urinalysis.
- On day 10, blood will be drawn for hematology and serum chemistry as detailed in [Section 6.6.2.1](#).
- After completion of all day 10 activities the subject will be discharged. A follow up visit may be scheduled on day 15 if clinically indicated. If a subject who withdraws consent prior to completion of all study activities, a follow up visit may be scheduled if clinically indicated.

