9.6.1 Adverse Events

Adverse events will be mapped to preferred term and body system using the Medical Dictionary for Regulatory Activities (MedDRA). The number and percentage of subjects reporting adverse events will be determined by relationship to treatment and by severity of the event. Drug-related adverse events will be considered those to be possibly related to bexagliflozin administration.

Adverse event listings will be provided for the following subsets:

- all treatment emergent AEs (TEAEs).
- all TEAEs at least possibly related to bexagliflozin.
- serious TEAEs (if any).
- TEAEs leading to study discontinuation (if any).

AEs are dosing emergent if they occur on or after bexagliflozin administration. TEAEs will be considered at least possibly related to bexagliflozin based on the investigator's assessment. Only TEAEs will be tabulated in summary tables. If the AE(s) onset date-time or date occurs after the first dose up until right before the next dose, the AE(s) will be assigned to the first treatment. Any AE(s) that occur after the second dose up until the follow-up visit will be assigned to the second treatment.

Tabulations will display TEAEs by severity and relationship to bexagliflozin.

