### 3. STUDY DESIGN

#### 3.1 Study Design

This single center, phase 1, open-label,  $2 \times 2$  crossover study is designed to assess the effects of a high-fat meal on the PK of orally administered bexagliflozin tablets. Eighteen (18) eligible healthy subjects will be randomized into two treatment groups such that an equal number ( $n = 9$ ) of subjects will receive a single oral dose of 20 mg of bexagliflozin with or without a meal on treatment day 1. Subjects randomized to receive bexagliflozin tablets with a high-fat meal on day 1 will receive a second dose of bexagliflozin tablets without a meal on treatment day 8 after an overnight fast. Subjects randomized to receive bexagliflozin tablets without a meal on treatment day 1 after an overnight fast will receive a second dose of bexagliflozin tablets with a high-fat meal on treatment day 8.

Bexagliflozin will be taken orally with 240 mL of water in the morning (approximately 8 a.m. to 10 a.m.). The time of dosing for a given subject will be the same (as far as practicalities permit) in both treatment periods.

The high-fat meal will follow the FDA guidance (Food and Drug Administration 2002) on high-fat (50% of total caloric content of the meal) and high-caloric (800 to 1000 calories) content. An example of the high-fat meal would be two eggs fried in butter, two strips of bacon, two slices of toast with butter, four ounces of hash brown potatoes and eight ounces of whole milk. Substitutions in this meal can be made as long as the meal provides a similar amount of calories from protein, carbohydrate, and fat and has comparable meal volume and viscosity.

Subjects dosed in the fed state will receive a 20 mg oral bexagliflozin tablet 30 min after starting to consume a high-fat meal after an overnight fast. No additional food should be allowed for at least 4 h post-dose. Water will be allowed as desired except for one hour before and after drug administration. The meal will be ingested in its entirety over an approximate 25-minute period, such that it is completed at least 5 minutes prior to the scheduled time of bexagliflozin dosing for the fed state treatment. If for some reason, a portion of the meal is not consumed, the reason and the amount of remaining food will be recorded. Subjects should receive standard meals at approximately the same time in each period of the study.

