### 6.1.1 Study Day and Visit Window Definitions

**Table 2. Time Windows for Safety Assessments**

Time Windows for Safety Assessments			
Scheduled Visit Number	Visit (label)	Time Interval (day)	Target Time Point (day)
1	Screening	-28 to -1	-28 to -1
2	Day 1	1	1
3	Day 2	2	2
4	Day 3	3-6	3
5	Day 7	7	7
6	Day 8	8	8
7	Day 9	9	9
8	Day 10	10	10

Data obtained during unscheduled visits will be allocated to the scheduled visit corresponding to the visit window they fall in as specified in Section 6.1.1. Safety data obtained during unscheduled time points will be allocated to the scheduled time point corresponding to the time window in which they fall. Data will be analyzed based on the nominal visits and nominal time points. If the data from the nominal visit or time point is missing, data from unscheduled visits for the same nominal visit or time point will be used. If multiple unscheduled assessments fall in the same visit window or time point, the non-missing assessment closest to target time point will be selected for analysis.

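### The by-treatment adverse event tables pool at least 168 h after the first dose with about 48 h after the second, which dilutes any fed-fasted difference, and protocol and SAP end the second window differently

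*SAP*

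**What the plan says.** - **First window.** SAP 6.3.3 assigns an event to the first treatment "If the AE(s) onset date-time or date occurs after the first dose up until right before the next dose". Under SAP 3.1 the first dose is on Day 1, and subjects who were fed first "will receive a second dose of bexagliflozin tablets without a meal on treatment day 8 after an overnight fast". The other group has the reverse order on the same days. The protocol synopsis makes the washout at least 7 days.
- **Second window, SAP 6.3.3.** "Any AE(s) that occur after the second dose up until study termination will be assigned to the second treatment". The term for the end point is not defined. The schedules in SAP 3.6 and Protocol Appendix 1 both mark study termination on Day 10.
- **Second window, Protocol 9.6.1.** "Any AE(s) that occur after the second dose up until the follow-up visit will be assigned to the second treatment". Protocol 7.7 says of that visit: "A follow up visit may be scheduled on day 15 if clinically indicated".
- **Tables.** SAP 6.3.3 and 8.4.1 present TEAE incidence by treatment, pooled over two sequences randomized 1:1 (nine each). SAP 3.3 plans no formal hypothesis test.
- **Later events.** SAP 6.3.3.1 gives the TEAE definition no end date. Protocol 6.9.4.2 requires active SAE monitoring for at least 14 days after discharge.

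The SAP text sets no common post-dose window and makes no adjustment for observation time. The table shells are in a separate document that was not available, so a restriction there cannot be ruled out.

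**The concern.** Safety in the fasted and fed states is a secondary objective, and the by-treatment TEAE tables are where a reader will look for it. The two attribution windows differ 3.5-fold in length. The extra time in the longer one lies wholly after the in-clinic post-dose stay, when little drug should remain in plasma. Two things are at stake:

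- whether a real difference shortly after dosing would show clearly in the tables;
- whether every TEAE after Day 10 belongs to a treatment. Under the SAP rule, read with Day 10 as termination, a later serious event is still treatment-emergent but falls to neither treatment. Under the protocol rule, the second window is longer only for subjects thought to need a visit.

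**Working it through.** The documents give no window length in hours, event rate or power for safety, so there is no stated figure to reproduce.

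**1. Window lengths** (SAP 3.1, SAP 3.6, Protocol 7.7)
- First dose: (8 − 1) × 24 = 168 h, a minimum.
- Second dose, to Day 10: (10 − 8) × 24 = 48 h. Ratio 168/48 = 3.5.
- Second dose, if a Day 15 visit is held and the protocol rule applies: (15 − 8) × 24 = 168 h, for that subject only.
- SAEs only: 48 + 14 × 24 = 384 h after the second dose.

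**2. Time in each treatment column, nine completers per sequence**
- Fed: 9 × 168 + 9 × 48 = 1944 h. Fasted: the same. Ratio 1.0.
- Common 0-48 h window: 18 × 48 = 864 h (44%).
- First-dose washout: 9 × 120 = 1080 h (56%).
- Protocol section 1 gives mean half-lives of 7.80 to 9.71 h, so the washout part starts 48/9.71 = 4.9 to 48/7.80 = 6.2 mean half-lives after dosing.

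**3. Dilution at perfect balance.** Assume a constant background hazard with 48 h risk p, and suppose food doubles the hazard in the first 48 h only.
- Background risk over 168 h: 1 − (1 − p)^3.5.
- Fed risk: 1 − (1 − p)^2 over 48 h and 1 − (1 − p)^4.5 over 168 h.
- Each column is the average of its 168 h and 48 h risks.

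For p = 10%, the fed column is (0.378 + 0.190)/2 = 0.284 and the fasted column is (0.308 + 0.100)/2 = 0.204, a ratio of 1.39. With a common 48 h window it is 0.190/0.100 = 1.90.

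| p (assumed) | Ratio, common 48 h | Ratio, planned | Difference, common 48 h (points) | Difference, planned (points) |
|---|---|---|---|---|
| 5% | 1.95 | 1.42 | 4.8 | 4.5 |
| 10% | 1.90 | 1.39 | 9.0 | 8.0 |
| 20% | 1.80 | 1.34 | 16.0 | 12.6 |
| 30% | 1.70 | 1.29 | 21.0 | 14.8 |

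**4. Unequal dropout.** Suppose two Group 2 subjects (fasted first) leave before the second dose, are not replaced, and are followed for the full first window.
- Fed: (9 × 168 + 7 × 48)/16 = 115.5 h per dosed subject.
- Fasted: (9 × 168 + 9 × 48)/18 = 108 h. Ratio 1.07.
- With no food effect and p = 10%, incidence is (9 × 0.308 + 7 × 0.100)/16 = 0.217 fed against 0.204 fasted, or 1.3 points. Over p = 5% to 30% the gap is 0.7 to 2.6 points.

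**5. With a common 0-48 h window**, each completer contributes 48 h per treatment and each column holds 864 h when all 18 complete. Among completers the two columns stay equal whatever the sequence split.

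**The case against.** The strongest reply is that no planned table makes a within-subject comparison of adverse events. Window length goes with period, and 1:1 sequences put the same mix of long and short windows in each column. The tables are descriptive, every event is listed, and Protocol 9.6.1 also tabulates by relationship to drug. Attribution up to the next dose keeps delayed events in the main table. Non-safety dropouts may be replaced, so the dropout case is narrow.

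Most of this stands. A reader might infer from the 3.5:1 ratio that the fed-fasted comparison is itself partly a comparison of observation time. At nine per sequence it is not: expected incidence under no food effect is equal (20.4% in each column at p = 10%). The striking contrast, 30.8% against 10.0% at that rate, is first dose against second dose, which no listed summary makes. For serious events, collection runs the other way (384 h against 168 h). The visit windows in SAP Table 2 and the differing end dates for medication recording might look like part of the same problem, but neither enters TEAE incidence, because events are assigned by onset.

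Three things survive. Balance does not remove dilution, and tabulation by relationship is not among the three summaries that SAP 8.4.1 names. Subjects who discontinue for safety are not replaced (Protocol 6.11), and a replaced subject who was dosed remains in the Safety Population, so balance is not guaranteed. The two ends of the second window do conflict.

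**Conclusion.** The point holds as one of dilution and inconsistent definition, not of bias at full enrolment. With nine completers per sequence, 56% of the time in each column is washout. Under the assumptions above, a true early doubling would appear as a ratio of 1.29 to 1.42 and not 1.70 to 1.95. The absolute difference shrinks less, by 0.3 to 6.2 points. Two unreplaced departures from one sequence add about 7% in time per subject and 1 to 3 points of incidence.

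These sizes rest on a constant background hazard, on assumed 48 h risks of 5% to 30%, and on reading study termination as Day 10. That washout events are mainly background is an inference from mean plasma half-lives. The objective is descriptive and secondary, and the primary PK analysis is unaffected. The change is worth making because it uses data already planned for collection.

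**What to change.** 1. In SAP 6.3.3 and 8.4.1, keep the all-TEAE summary by treatment, but split it by onset: 0-48 h after each dose, and later than 48 h. Use the 0-48 h part for the fed-versus-fasted comparison, and show the later part by period or sequence. Keep all events in the listings.
2. Give the second window the same end in Protocol 9.6.1 and SAP 6.3.3, define that end, and word it so that any TEAE after Day 10, including one found during SAE monitoring, is assigned to a treatment.

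The cost is SAP wording, one aligned sentence in the protocol and one extra split in the tables, with no new data. The downside is that late-onset events fall outside the 0-48 h comparison. They remain visible in the second part and in the all-TEAE summary.

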### **6.3.3.1 Treatment-Emergent AE (TEAE)**

An adverse event is considered treatment-emergent if the date of onset is on or after the date of first dose of study medication, or worsens during the treatment period (intensity/severity grades worsen).

### **6.3.3.2 Serious Adverse Events (SAE)**

AEs will be categorized as serious or non-serious using the definition specified in Section 6.9 of the study protocol.

### **6.3.3.3 Immediately Reportable AE (IRAE)**

Any serious adverse event or any adverse event that necessitates discontinuation of the study drug.

### **6.3.3.4 Adverse Events Counting Rules**

1. A subject with more than one different AE in a particular system organ class (SOC) will be counted only once in the total of subjects experiencing adverse events in that particular SOC.
2. A subject having experienced the same event (AE preferred term) more than once during the study will be counted only once in the number of subjects with that event.
3. A subject having experienced the same event (AE preferred term) more than once during the study with a different severity or seriousness, it will be counted only once with the worst grade and seriousness respectively.
4. A subject having experienced the same event (AE preferred term) more than once during the study with a different causal relationship to the study drug, it will be counted only once by considering the most-related documented degree of relationship.

### **6.3.3.5 AE Severity**

Adverse events will be graded on a 3-point scale and reported as indicated on the CRF. The intensity of an adverse experience will be graded as “Mild”, “Moderate”, and “Severe” using the criteria specified in Section 6.9 of the study protocol.

### **6.3.3.6 Relationship to the Investigational Medicinal Product**

The relationship of an AE to dosing will be assessed as “Definite”, “Probable”, “Possible”, “Not Likely”, or Unrelated using the criteria specified in Section 6.9 of the study protocol.

### **6.3.3.7 AE with Irregular Start/End Dates**

Partial dates may be imputed when appropriate. Imputed dates will be used to determine Study Day.

If a partial date is reported for the start of an AE, a complete date will be imputed by the following algorithm:

1. Only the year is reported: If the subject started receiving study medication in the previous year, then January 1 will be used as the starting date of the event. If the subject started receiving study medication in the year reported, then the date of the first dose of study medication will be used as the start of the event.
2. The month and year is reported: If the subject started receiving study medication prior to the month and year reported, then the first day of the month will be used as the starting date of the event. If the

subject started receiving study medication during the month and year reported, then the date of the first dose of study medication will be used as the start of the event.

If a partial date is reported for the end of an adverse event and the adverse event is not continuing, a complete date will be imputed by the following algorithm:

1. Only the year is reported: If the subject started receiving study drug in the previous year, then the date of final study contact with the subject will be used as the end of the adverse event. If the subject started receiving study medication in the year reported, then the earlier of December 31 or the date of final study contact with the subject will be used as the end of the adverse event.
2. The month and year reported: The earlier of the last date of the month or the date of final contact with the subject will be used as the end of the AE.

The above rules are subject to logical sense, for example, imputed start date should be on or prior to imputed end date.

All AEs will be included in the tabulations regardless the completeness of the onset dates.

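### The partial-date rule for adverse events uses only the first dose, so most Period 2 events with a missing onset day would be counted under the Period 1 treatment

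*SAP*

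**What the plan says.** SAP 6.3.3.7 gives the algorithm for incomplete adverse-event start dates.

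- Month and year known, first dose in that month: "subject started receiving study medication during the month and year reported, then the date of the first dose of study medication will be used".
- Month and year known, first dose in an earlier month: "If the subject started receiving study medication prior to the month and year reported, then the first day of the month will be used".
- Only the year known, first dose in that year: "subject started receiving study medication in the year reported, then the date of the first dose of study medication will be used as the start". If dosing began in the previous year, January 1 is used.

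The second dose is not mentioned in any branch. The section also keeps every such event in the tables: "All AEs will be included in the tabulations regardless the completeness of the onset dates".

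SAP 6.3.3 decides the treatment from the onset date. If the "onset date-time or date occurs after the first dose up until right before the next dose, the AE(s) will be assigned to the first treatment". For the rest: "Any AE(s) that occur after the second dose up until study termination will be assigned to the second treatment". Protocol 9.6.1 uses the same split but ends the second window at the follow-up visit: "Any AE(s) that occur after the second dose up until the follow-up visit will be assigned to the second treatment".

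SAP 6.3.3 and 8.4.1 present the incidence of treatment-emergent events by treatment, that is, by fed and fasted condition.

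**The concern.** The algorithm suits a study with one treatment, where the first dose separates pre-treatment from on-treatment events and nothing later matters. Here every subject is dosed twice, 7 days apart, and the imputed date also decides which meal condition an event is counted under. An event that began after the second dose, but whose day was not recorded, will usually be given a date before that dose.

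Evaluating safety in the fasted and fed states is a secondary objective (Protocol 2.2, SAP 2.2), and with 18 subjects one misplaced event is visible in a by-treatment table. The plan would also pass over whatever the record shows about when the event was first reported.

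**Working it through.** The documents give no figure on this point, so there is nothing to reproduce. The check applies the two SAP rules to the calendar.

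**Inputs**
- Second dose 7 days after the first (Days 1 and 8; SAP 3.1).
- Discharge and study termination on Day 10 (Protocol 7.7, SAP 3.6).
- Optional follow-up visit on Day 15 (Protocol 7.7).
- Serious-event monitoring for at least 14 days after discharge (Protocol 6.9.4.2): 10 + 14 = Day 24.
- Assumptions: first-dose dates uniform over the 1,461 days of 2016-2019; onset days uniform within each window; an imputed onset on the second-dose date counted as Period 2, the reading kindest to the SAP.

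**Rule.** Let d1 be the first-dose date, d2 = d1 + 7, and x = d2 + e the true onset, with e = 0 on Day 8. With month and year known, the imputed onset is d1 if x is in the same month as d1, and otherwise the first of x's month. The event stays in Period 2 only if the first of a month falls between d2 and x inclusive, a span of e + 1 days. Four years contain 48 month starts, so for each e, 48 × (e + 1) of the 1,461 first-dose dates give the right answer.

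| True onset | Cases | Kept in Period 2 | Wrong treatment |
|---|---|---|---|
| Days 8-10 | 3 × 1,461 = 4,383 | 48 × (1+2+3) = 288 | 4,095 (93.4%) |
| Days 8-15 | 8 × 1,461 = 11,688 | 48 × (1+…+8) = 1,728 | 9,960 (85.2%) |
| Days 8-24 | 17 × 1,461 = 24,837 | 48 × (1+…+17) = 7,344 | 17,493 (70.4%) |

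If an imputed onset on the second-dose date is not counted as Period 2, the shares are 96.7%, 88.5% and 73.7%. If only the year is known, they are 99.5%, 98.8% and 97.5% (tie counted as Period 2).

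**Direction.** For an event after the first dose, the rule never gives an onset later than the true one. A Period 1 event therefore cannot move to Period 2; enumeration over 365 first-dose dates found 0 such cases.

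**Effect on the fed-fasted contrast.** Take 9 subjects per sequence, event rates F (fed) and S (fasted) that are the same in both periods, and a share m of Period 2 events misplaced.
- Expected fed count = 9F + 9Sm + 9F(1 − m).
- Expected fasted count = 9S + 9Fm + 9S(1 − m).
- Difference = 18(F − S)(1 − m).

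Since m cannot exceed 1, the expected difference shrinks but does not change sign. As an illustration with assumed values F = 0.3, S = 0.1 and 10% of Period 2 events partially dated, m = 0.10 × 0.934 = 0.0934. The expected counts become 5.23 fed and 1.97 fasted, a difference of 3.26 instead of 3.60. The period totals, truly 3.60 each, become 3.60 + 9 × 0.4 × 0.0934 = 3.94 and 3.26. At an assumed 5% or 25% partially dated, the fed-fasted difference is 3.43 or 2.76.

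**Per subject.** With 18 subjects dosed in each condition, one misplaced subject changes incidence by at most 1/18 = 5.6 percentage points in each treatment.

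**The case against.** **The wording is permissive.** SAP 6.3.3.7 says that dates may be imputed where appropriate, names Study Day as the use of the result, and makes the rules subject to logical sense. A careful programmer could decline to date a known post-second-dose event to Day 1. However, SAP 6.3.3 assigns treatment by onset date, and no other rule covers a partial date that must still be tabulated. The only example of logical sense is that the start should not follow the end, and an onset set too early satisfies it. If another rule is intended, it is not written down.

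**Partial dates should be rare where the rule fails most.** Subjects are confined from Day 7 until 48 h after the second dose, and adverse events are checked on Days 7, 8, 9 and 10. A missing day is more plausible between the Day 3 discharge and Day 7, where assignment to the first treatment is correct, or after Day 10, where the error share is lower. This stands. A reader might infer that nearly every incompletely dated Period 2 event is misplaced. With month and year known, that describes only Days 8-10; the share falls to 85% and 70% in the wider windows.

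**Nothing formal depends on it.** SAP 3.3 plans no hypothesis tests, the safety tables are descriptive, and all events are listed by subject. This also stands, and it limits the point to a minor one.

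**The record may not show the visit.** The annotated CRF is not among the documents, so it cannot be assumed that the adverse-event form captures the visit or period of first report. The fix has to allow for that.

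**Conclusion.** The concern holds as a defect in a stated rule, of small practical weight. As written, SAP 6.3.3.7 and 6.3.3 together place most Period 2 events with a missing onset day under the Period 1 treatment, in the proportions tabulated above. Those proportions rest on uniform first-dose dates and onset days, and on applying the algorithm literally.

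Two stronger readings are not supported.
- One might infer a bias toward one meal condition, because the error runs in one direction. The direction is by period. With 1:1 allocation (SAP 3.2), both fed and fasted events move, so the expected result is dilution and a false period effect. A single misplaced event can still go against either condition by chance.
- One might infer that each misplaced subject always shifts incidence by 1/18 down in one column and up in the other. SAP 6.3.3.4 and 8.4.1 count a subject once per preferred term and system organ class. If the subject already has that event in Period 1, or has another in Period 2, one or both shifts vanish. The 1/18 is a ceiling and assumes that all 18 are dosed in both periods.

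The documents give no rate of partial dates, so the number of events affected cannot be stated; it is probably small. The primary PK analysis does not use these dates.

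**What to change.** Amend SAP 6.3.3.7 before database lock. Where a partial start date is compatible with both periods, impute the date of the last dose given before the event was first recorded. Take the order from the period, visit or entry date on the adverse-event record if the CRF captures one of these, and otherwise from the event's end date or the source record. If the order cannot be established, flag the event in a footnote to the by-treatment tables and do not default it to the first treatment. State in the same place that the imputed date is used for treatment assignment as well as Study Day.

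The rule presumes that an event not reported on Day 7 or before dosing on Day 8 began after the second dose. That is reasonable given the scheduled checks, but it should be stated.

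The cost is a short addition to the SAP, a small amount of programming, and some data review for the few events concerned. No new data collection is needed if the record or source shows when the event was first reported.
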